**ML39355_STATISTICAL ANALYSIS PLAN_Final 2.0_17 June 2020**

before Week 26; Decline of $< 10\%$ to 0% ; Improvement of $\geq 0\%$) (absolute change in FVC % predicted and relative change for volume) will be provided in frequency table.

Additionally, the absolute change in FVC from Baseline at Week 12, 39 (optional) and 52 (optional) and mean FVC values through all time points (both in mL and % predicted) will be summarized (without missing value imputation) in tables with standard descriptive statistics for continuous variables and 95% CI for the means and mean changes. For each time point, descriptive analysis will be repeated for values within visit window.

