Treatment with pirfenidone will continue until Week 26 (± 1). Patients will be followed through the Follow-up visit scheduled 2-4 weeks after treatment completion or until entry into the long-term follow-up (rollover study), whichever occurs earlier. Patients who undergo lung transplantation or who chose to withdraw from study procedures early will be followed for vital status until Week 26. If patients discontinue study treatment early for any reason, they should continue with all scheduled study procedures through Week 26.

Patients who complete participation in the study prematurely due to any reasons (drop-outs) will not be replaced.

[figure not shown]
Patients who proceed until Week 26 in the study and are compliant with the study treatment, may continue treatment with commercially available pirfenidone after study completion in real clinical practice (long-term follow-up or rollover study). In this case, patients will have two follow-up assessments of FVC and 6MWT at Weeks 39 and 52 and CT scans evaluation at Week 52. Information on AEs occurrence will also be collected during the rollover part of the study.

If a patient cannot participate in the rollover part of the study for any reason, a follow-up visit will be performed 14-28 days after the last dose of pirfenidone is taken.

Pirfenidone—F. Hoffmann-La Roche Ltd

The study schema is presented in [Figure 1](#) below. A schedule of activities is provided in [Appendix 1](#).

Figure 1 Study Schema

An Independent Data Monitoring Committee (IDMC) will be implemented in the study. The IDMC will conduct regular review of the trial safety data, with the focus on death cases, serious adverse events, unexpected adverse events, adverse events leading to treatment or study discontinuation, liver enzyme increases, reported as adverse events, and other AEs immediately reported to the Sponsor (see [Section 5.2.3.2](#)).

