4.6 PATIENT, TREATMENT, STUDY, AND SITE DISCONTINUATION

4.6.1 Patient Discontinuation

Patients have the right to voluntarily withdraw from the study at any time for any reason. In addition, the investigator has the right to withdraw a patient from the study at any time if it is considered to meet patients' interests best and approved by the Sponsor.

Reasons for withdrawal from the study may include, but are not limited to, the following:

- Patient withdrawal of consent at any time
- Any medical condition that the investigator or Sponsor determines may jeopardize the patient's safety if he or she continues in the study
- Investigator or Sponsor determines it is in the best interest of the patient for other reasons
- Protocol deviation (at Sponsor's discretion) (e.g. refusal to follow study requirements)

Generally poor compliance in the study will not be treated as a sufficient reason for patient's early discontinuation from the study. However, non-compliant patients cannot proceed in the rollover part of the study, where treatment with pirfenidone is continued in a routine clinical setting.

Every effort should be made to obtain information on patients who withdraw from the study. The primary reason for withdrawal from the study should be documented on the appropriate eCRF. However, patients will not be followed for any reason after consent has been withdrawn. Patients who withdraw from the study will not be replaced.

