Treatment with pirfenidone will continue until Week 26 (\pm 1). Patients will be followed through the Follow-up visit scheduled 2-4 weeks after treatment completion or until entry into the long-term follow-up (rollover study), whichever occurs earlier. Patients who undergo lung transplantation or who chose to withdraw from study procedures early will be followed for vital status until Week 26. If patients discontinue study treatment early for any reason, they should continue with all scheduled study procedures through Week 26.

Patients who complete participation in the study prematurely due to any reasons (drop-outs) will not be replaced.

Patients who proceed until Week 26 in the study and are compliant with the study treatment, may continue treatment with commercially available pirfenidone after study completion in real clinical practice (long-term follow-up or rollover study). In this case, patients will have two follow-up assessments of FVC and 6MWT at Weeks 39 and 52 and CT scans evaluation at Week 52. Information on AEs occurrence will also be collected during the rollover part of the study.

If a patient cannot participate in the rollover part of the study for any reason, a follow-up visit will be performed 14-28 days after the last dose of pirfenidone is taken.

A schedule of activities is provided in Table 1.

An Independent Data Monitoring Committee (IDMC) will be implemented in the study. The

ML39355_STATISTICAL ANALYSIS PLAN_Final 2.0_17 June 2020

IDMC will conduct regular review of the trial safety data, with the focus on death cases, serious adverse events, unexpected adverse events, adverse events leading to treatment or study discontinuation, liver enzyme increases, reported as adverse events, and other AEs immediately reported to the Sponsor.

Duration of participation in the study for an individual patient is between 31 and 35 weeks (excluding long-term follow-up). For patients continuing in the rollover study the duration of participation in the study extends up to maximum 58 weeks.

ML39355_STATISTICAL ANALYSIS PLAN_Final 2.0_17 June 2020

Study period	IC Visit	Screening (Washout, if applicable)	Treatment period									Follow-Up	Long-Term Follow-Up ¹⁶		
			Day 1	W1 (± 1 d)	W2 (± 2 d)	W4 (± 2 d)	W8 (± 2 d)	W12 (± 1 w)	W16 (± 1 w)	W20 (± 1 w)	W26 (± 1 w)		14–28 days after last dose	W39 (± 2 w)	W52 (± 2 w)
Week (Window)		-4 to -1													
Borg scale ¹³		x	x					x			x	x		x	x
EQ-5D questionnaire ¹³		x	x					x				x			x

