¹² Pregnancy test must be performed before first dosing on Day 1 and must be negative. If the urine test is positive, serum pregnancy test must be performed.

¹³ Questionnaires should be self-administered before the patient or clinician receives any information on disease status, prior to the performance of non-PRO assessments, and prior to the administration of study treatment, with the exception for Borg scale administered in conjunction with the 6MWT.

¹⁴ Patient diary should be filled out on daily basis by the patient and reviewed by the investigator at in-clinic visits. Patient diary captures information on compliance and AEs occurrence and is dispensed as needed.

¹⁵ Schedule of calls in IPF Care Program you can see in Appendix 7

¹⁶ Only in patients continuing treatment with pirfenidone in real clinical practice.

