16.1. Tables

Patients Disposition

- Table 1.1 Patients disposition (All Enrolled patients)
- Table 1.2 Violation of eligibility criteria (Screening Failures)
- Table 1.3 Analysis populations (Allocated to treatment set)
- Table 1.4 Study visits

Protocol Deviations

- Table 1.5 Protocol deviations / violations (Allocated to treatment set)

Demographic and Anthropometric characteristics

- Table 1.6 Demographic characteristics (TS)
- Table 1.7 Anthropometric characteristics (TS)

Baseline Variables

- Table 1.8 Surgical lung biopsy (TS)
- Table 1.9 HRCT for patient eligibility confirmation (TS)
- Table 1.10 Carbon monoxide diffusing capacity (DLCO) (TS)
- Table 1.11 Pre- and post-bronchodilator spirometry parameters at screening (TS)
- Table 1.12 Serologic tests (TS)
- Table 1.13 GAP assessment (TS)
- Table 1.14 Review transbronchial lung biopsy/BAL (TS)

Medical history

- Table 1.15 Prior medical/surgical conditions/diagnoses (TS)
- Table 1.16 Concurrent medical/surgical conditions/diagnoses (TS)
- Table 1.17 History of idiopathic pulmonary fibrosis (TS)

Prior and concomitant medications

- Table 1.18 Prior medications (TS)
- Table 1.19 Concomitant medications (TS)
- Table 1.20 Concomitant medications during rollover study (TS)

Efficacy Analyses

- Table 2.1 Descriptive statistics for FVC by visit (FAS)
- Table 2.2 Primary efficacy endpoint (FAS)
- Table 2.3 Primary efficacy endpoint: categorical results (FAS)
- Table 2.4 Primary efficacy endpoint by pattern type (CSS)
- Table 2.5 6-Minute Walk Test (FAS)
- Table 2.6 Change in 6MWT distance at Week 26 by category (FAS)
- Table 2.7 Borg scale (FAS)
- Table 2.8 EQ-5D-5L. Descriptive statistics (FAS)
- Table 2.9 Change in EQ-5D-5L. Mobility (FAS)
- Table 2.10 Change in EQ-5D-5L. Self-Care (FAS)
- Table 2.11 Change in EQ-5D-5L. Usual Activities (FAS)
- Table 2.12 Change in EQ-5D-5L. Pain/Discomfort (FAS)
- Table 2.13 Change in EQ-5D-5L. Anxiety/Depression (FAS)
- Table 2.14 EQ-5D-5L. VAS and Index score (FAS)
- Table 2.15 HRCT. HRCT fibrosis score (FAS)
- Table 2.16 HRCT. Lung opacity score (FAS)
- Table 2.17 Exacerbation cases during treatment period (FAS)
- Table 2.18 Exacerbation cases during rollover study (FAS, patients continuing in the rollover study)
- Table 2.19 Exacerbation cases during whole study period (FAS, patients continuing in the rollover study)

Safety Analyses

- Table 3.1 Duration of exposure (TS)
- Table 3.2 Total number of capsules taken (TS)

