SD	XX.XX	XX.XX
Median	XX.X	XX.X
Min	XX	XX
Max	XX	XX

N: the number of patients in the FAS.

n: the number of valid measurements.

Baseline FVC is the average of the pre-bronchodilator FVC measured at the Screening and Day 1 visits. The FVC at Week 26 is the average of the FVC measured on two separate days at Week 26.

*: Values assessed within the corresponding visit window.

Path to the program code, date and time of output

Data extracted: DD.MM.YYYY

<Report the following assessments: Screening (pre-bronchodilator), Day 1, Baseline, Week 12, Week 26 Day 1, Week 26 Day 2, Week 26, Week 39, Week 52>
 <FVC values within the visit window will also be presented descriptively for the following assessments: Week 12*, Week 26 Day 1*, Week 26 Day 2*, Week 26*, Week 39*, Week 52*>
 <Report the following parameters: FVC (absolute), mL/ FVC (relative) predicted, %>

ML39355_STATISTICAL ANALYSIS PLAN_Final 2.0_17 June 2020

 F. Hoffmann-La Roche Ltd
 ML39355

Table 2.2 Primary efficacy endpoint
 Full analysis set (FAS)
 Page X of X

Parameter: XXXXXXXXXXXX, <units>

	Total (N = XX)	Change from the baseline
Baseline		
n	XX	
Mean [95% CI]	XX.X [XX.X - XX.X]	
SD	XX.XX	
Median	XX.X	
Min	XX	
Max	XX	
Week 26, Primary analysis		
n	XX	XX
Mean [95% CI]	XX.X [XX.X - XX.X]	XX.X [XX.X - XX.X]
SD	XX.XX	XX.XX
Median	XX.X	XX.X
Min	XX	XX
Max	XX	XX
Week 26, Sensitivity analysis 1		
n	XX	XX
Mean [95% CI]	XX.X [XX.X - XX.X]	XX.X [XX.X - XX.X]
SD	XX.XX	XX.XX
Median	XX.X	XX.X
Min	XX	XX
Max	XX	XX
Week 26, Sensitivity analysis 2		
n	XX	XX
Mean [95% CI]	XX.X [XX.X - XX.X]	XX.X [XX.X - XX.X]
SD	XX.XX	XX.XX
Median	XX.X	XX.X
Min	XX	XX
Max	XX	XX
...		

N: the number of patients in the FAS.

ML39355_STATISTICAL ANALYSIS PLAN_Final 2.0_17 June 2020

n: the number of valid measurements.

Baseline FVC is the average of the pre-bronchodilator FVC measured at the Screening and Day 1 visits. The FVC at Week 26 is the average of the FVC measured on two separate days at Week 26.

Sensitivity analyses 1 - 6 related to missing Week 26 data imputation are described in SAP Section 8.1; Sensitivity analysis 7 - Primary analysis excluding all FVC values outside of visit window. Sensitivity analysis 8 - Complete case set; Sensitivity analysis 9 - Complete case set excluding all FVC values outside of visit window.

Path to the program code, date and time of output

Data extracted: DD.MM.YYYY

<Report the following parameters: FVC (absolute), mL/ FVC (relative) predicted, %>

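### The Week 26 and Week 39/52 rows of the by-visit efficacy tables describe different patients, and no row shows how the rollover patients stood at Week 26

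*SAP*

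**What the plan says.** After the primary analysis, SAP 8.1 adds: "Additionally, the absolute change in FVC from Baseline at Week 12, 39 (optional) and 52 (optional) and mean FVC values through all time points". The sentence continues that these "will be summarized (without missing value imputation) in tables with standard descriptive statistics for continuous variables". The output is Table 2.1, an FAS table with no rollover restriction. Its shell note lists the assessments as "Screening (pre-bronchodilator), Day 1, Baseline, Week 12, Week 26 Day 1, Week 26 Day 2, Week 26, Week 39, Week 52". Each row prints n and the mean, and the post-baseline rows also print the change from the patient's own baseline.

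On who can have late values, SAP 4.1 says: "Patients who proceed until Week 26 in the study and are compliant with the study treatment, may continue treatment with commercially available pirfenidone". Protocol 4.6.1 adds that "non-compliant patients cannot proceed in the rollover part of the study". Footnote 16 of the schedule qualifies the long-term follow-up columns: "Only in patients continuing treatment with pirfenidone in real clinical practice". By contrast, Protocol 3.1 and SAP 4.1 ask patients who stop drug early to complete all procedures through Week 26, so they can contribute to the Week 26 row.

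The SAP does restrict the denominator elsewhere. Tables 2.18 and 2.19 (exacerbations) and the rollover adverse event tables are limited to patients continuing in the rollover study. The continuous efficacy tables are not.

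**The concern.** A table that runs Baseline, Week 12, Week 26, Week 39, Week 52 under one FAS heading invites the reader to follow it as the course of one cohort. From Week 26 to Week 52 it is not one cohort. Patients who stopped drug, were non-compliant or did not continue leave the table at Week 26, and patients who die or are lost afterwards leave later. SAP 6.3 itself assumes that the unobserved FVC of patients who die would be lower than that of survivors, so this loss may well be informative.

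What is at stake is any statement that lung function, walking distance, breathlessness, quality of life or HRCT score held steady after Week 26. The study has no comparator against which to check such a statement. The same layout is used in Tables 2.5 (6MWT), 2.7 (Borg), 2.14 (EQ-5D VAS and index), 2.15 (HRCT fibrosis score) and 2.16 (lung opacity). In Table 2.15 the p-values for Week 26 and Week 52 are each paired with baseline, but possibly in different patients.

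**Working it through.** **What the tables give.** For the Week 52 row, mean minus mean change equals the Baseline mean of those same patients. This needs every treated patient to have a baseline, which is expected: screening %FVC is an entry criterion, and SAP 8.1 uses whichever of Screening and Day 1 is available. So their Baseline can be recovered. Their Week 26 value cannot, from any planned summary table. Table 2.4 comes nearest, splitting Week 26 by whether drug was taken to Week 26, but that is not the rollover group.

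**Plan figures used as anchors** (Protocol 6.1, SAP 5). Reference change in % predicted FVC: 65.3 − 67.8 = −2.5. SD of change: 14.52 × √2 = 20.5, taken as 20. Half-width of the 95% CI for 60 patients: 1.96 × 20/√60 = 5.06, the plan's value of about 5. The plan gives no figure for the share rolling over.

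**Identity.** Let s be the share of patients with a Week 26 value who also have a Week 52 value. Let R and N be the mean Week 26 changes of those with and without a Week 52 value, and d the mean paired change from Week 26 to Week 52.

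- Week 26 row = sR + (1 − s)N
- Week 52 row = R + d
- Difference between rows = d + (1 − s)(R − N)

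The last term is the selection artefact. Examples, all with assumed group means and a Week 26 row of −2.5 (n = 60):

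- 48 at 0.0 and 12 at −12.5: artefact 0.2 × 12.5 = 2.5. With d = −2.5, Week 52 reads −2.5 and the loss is invisible.
- 50 at −1.0 and 10 at −10: (50 × −1.0 + 10 × −10)/60 = −2.5. With d = 0, Week 52 reads −1.0, an apparent gain of 1.5.
- 54 at −1.67 and 6 at −10: with d = −2.5, Week 52 reads −4.17. The rows show a loss of 1.67 of the true 2.5.

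**Range.** Suppose everyone truly loses a further 2.5 points, so the true Week 52 change is −5.0. Let the tendency to continue have correlation r with FVC change. The mean of those who continue is then shifted by r × SD × φ(z)/s, where z is the normal quantile at 1 − s. I use SD 20 (the plan's) and SD 8.7, since √(11.24² + 14.52² − 2 × 0.8 × 11.24 × 14.52) = 8.72 with an assumed baseline to Week 26 correlation of 0.8. The Week 52 columns take r = 0.5.

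| s | φ(z)/s | Week 52 row, SD 20 | Week 52 row, SD 8.7 | r that hides all 2.5: SD 20 | SD 8.7 |
|---|---|---|---|---|---|
| 90% | 0.195 | −3.05 | −4.15 | 0.64 | not possible |
| 80% | 0.350 | −1.50 | −3.48 | 0.36 | 0.82 |
| 70% | 0.497 | −0.03 | −2.84 | 0.25 | 0.58 |
| 60% | 0.644 | +1.44 | −2.20 | 0.19 | 0.45 |

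The comparison is with −2.5 in the Week 26 row. For mean level, take SD 14.52, s = 80%, r = 0.5 and a true Week 52 mean of 65.3 − 2.5 = 62.8. The row would read 62.8 + 0.5 × 14.52 × 0.350 = 65.3, the same as at Week 26.

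**The case against.** The case for leaving the tables alone is substantial. The FVC and 6MWT endpoints end at Week 26, and their later summaries are optional and additional. Every row prints n and the change from the patient's own baseline, so the Baseline to Week 52 change is already a proper within-patient estimate for those who continued. Rollover numbers are in Table 1.1, rollover status is in Listing 1 and FVC by visit is in Listing 18. Failure to continue need not mean decline: the sponsor does not supply drug after Week 26 (Protocol 4.3.4), and Protocol 3.1 allows non-participation for any reason. Shifts of 1.5 to 2.5 points also lie inside the plan's half-width of about 5.

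Most of this stands, and it keeps the point small. It does not supply the missing comparison. Own-baseline changes at Week 26 and Week 52 still come from different patients, mean levels are not paired at all, and a per-patient listing is not a summary. The half-width of 5 also depends on SD 20; with SD 8.7 it would be 1.96 × 8.7/√60 = 2.20. The HRCT exploratory endpoint does name Week 52.

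A reader might infer that Table 2.1 sets an imputed, full-cohort Week 26 against un-imputed late visits. The documents do not support this. The no-imputation wording in SAP 8.1 covers the means at all time points, so Week 26 in Table 2.1 is observed-only too. The imputed Week 26 result, with death set to zero, is in Table 2.2, which has no Week 39 or Week 52 rows. Deaths before Week 26 are therefore absent from both rows and cannot explain a difference between them.

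**Conclusion.** The point holds as a limited one about presentation. In Table 2.1, and likewise in Tables 2.5, 2.7 and 2.14 to 2.16, the rows after Week 26 describe a selected subset of the patients in the Week 26 row, and no planned row gives that subset at Week 26. Selection and later loss could mask a further decline.

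The stronger statement, that selection will make the course look stable, is not supported. The documents give neither a rollover rate nor any link between continuing and FVC, and every figure above beyond the plan's own rests on assumed values. With 90% continuing and the smaller SD, selection hides only part of a 2.5-point loss; with 70 to 80% continuing and the plan's SD of 20, a moderate correlation hides all of it. The primary Week 26 analysis is not touched.

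**What to change.** Add rows restricted to patients with Week 39 or Week 52 data:

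- Tables 2.1, 2.5 and 2.7: Baseline, Week 12 and Week 26.
- Table 2.14: the same three rows, for patients with Week 52 data, since EQ-5D is not scheduled at Week 39.
- Tables 2.15 and 2.16: Baseline and Week 26 only, for patients with Week 52 data, since no HRCT is scheduled at Week 12 or Week 39.

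In each table add the paired Week 26 to Week 52 change with n, mean, SD and 95% CI, and a footnote giving how many patients with a Week 26 value have no later value and why. State in SAP 8.1 to 8.3 that any description of the course after Week 26 rests on these rows.

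The cost is a few descriptive rows from data already collected and listed. SAP section 2 allows revision before database soft lock.

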8.2. Secondary Efficacy Analyses

eCRF form: “6-Minute Walk Test”, “BORG SCALE”, “EUROPEAN QUALITY OF LIFE 5-DIMENSION 5-LEVEL QUESTIONNAIRE”.

Change in 6MWT distance from Baseline to Week 26

Baseline 6MWT distance will be the average of the measurements recorded at the Screening and Day 1 visits. The 6MWT distance at Week 26 will be defined as the average of the 6MWT distance recorded on two separate days at Week 26. Data will be analyzed using standard descriptive statistics for continuous variables and 95% CI for the means and mean absolute changes.

The distribution (number and percentage) of 6MWT distance across three categories of change from Baseline (Decline of ≥ 50 m or death before Week 26; Decline of < 50 m to 0 m (exclusively), Improvement of ≥ 0 m) will be provided in frequency table.

Additionally, the absolute change in 6MWT from Baseline at Week 39 (optional) and Week 52 (optional) will be summarized in table with standard descriptive statistics for continuous variables and 95% CI for the mean.

Borg scale results will be presented descriptively by visit of assessment. Borg scale results (as a continuous variable) will be presented for both pre-test and post-test by visit of assessment and change from baseline (the average of the measurements recorded at the Screening and Day 1 visits) at post-baseline visits for pre-test assessments only.

The Borg scale results at Week 26 will be defined as the average of the Borg scale results recorded on two separate days at Week 26. If at baseline and/or at Week 26 for 6MWT distance or Borg scale either value is missing, the non-missing value will be used.

Descriptive analysis for 6MWT distance and Borg scale results will be repeated excluding assessments outside of visit window.

Change from Baseline to Week 26 in patients' quality of life as measured with EQ-5D-5L

- Cross tabulation for each of five dimensions (Mobility, Self-Care, Usual Activities, Pain / Discomfort, Anxiety / Depression) by response and study week.

ML39355_STATISTICAL ANALYSIS PLAN_Final 2.0_17 June 2020

- VAS score, including absolute changes from baseline, will be summarized with descriptive statistics by study week.
- EQ-5D-5L index score using the UK value set, including absolute changes from baseline, will be summarized with descriptive statistics by study week.

Descriptive analysis will be repeated excluding assessments outside of visit window.

The baseline assessment is the last non-missing assessment prior to the first dose of the study drug.

8.3. Exploratory Efficacy Analyses

eCRF form: “HRCT SCAN”, “ADVERSE EVENTS”.

HRCT fibrosis score

The HRCT findings will be evaluated using HRCT scoring system. One ILD radiologist will make assessments of 4 main findings in three zones of each lung. The six zone scores will be averaged to determine the total score for each patient. Score will be recorded at the initial diagnosis and after six and 12 months in a similar manner for further comparison. The mean \pm SD of HRCT fibrosis score like continuous variable will be determined obligatory at baseline, 6 months and optional at 12 months.

The values of HRCT fibrosis score at baseline, at Week 26 and Week 52 (optional) will be summarized in table with standard descriptive statistics for continuous variables and 95% CI for the mean.

Additionally, the absolute change of HRCT fibrosis score from baseline at Week 26 and Week 52 (optional) will be summarized in table with standard descriptive statistics for continuous variables and 95% CI for the mean.

The paired t-test will be performed to evaluate the changes in the variable from the baseline to Week 26 and Week 52 (optional), respectively. The type I error rate will be set to 5%.

Lung opacity (ground-glass attenuation)

The sign ‘lung opacity’ will be qualified separately using methodology described above for other signs, and its change over time will be assessed outside the framework of a total summed index of fibrosis (HRCT fibrosis score). Lung opacity should be graded as reticular abnormality to calculate the score for each zone, i.e. the percentage (%) area of opacity in a zone should be multiplied by the score of 2.

The lung opacity score at Baseline, at Week 26 and Week 52 (optional) will be summarized using standard descriptive statistics for continuous variables and 95% CI for the mean.

Additionally, the absolute change of lung opacity score from Baseline at Week 26 and Week 52 (optional) will be summarized in table with standard descriptive statistics for continuous variables and 95% CI for the mean.

**ML39355_STATISTICAL ANALYSIS PLAN_Final 2.0_17 June 2020**Exacerbations

An exacerbation will be defined as an AE with special criteria “Is this an exacerbation of IPF?” = “Yes”, i.e. only in case the exacerbation has led to death of a patient. Rate of exacerbation will be reported in three following tables:

- Exacerbation cases during treatment period (until Week 26).
- Exacerbation cases during long-term follow-up period (from Week 26 to Week 52).
- Exacerbation cases during whole study period (from Day 1 to Week 52, applicable only for patients continuing in the rollover study).

Exacerbation cases will be listed.

The treatment period and rollover period for the analysis of exacerbations will be defined similarly to Section 9.2.

9. Safety Analyses**9.1. Exposure**

Exposure will be evaluated based on the information from the “ASSESSMENT OF COMPLIANCE”, “STUDY DRUG ADMINISTRATION (TREATMENT PERIOD)”, “COMMERCIALY AVAILABLE PIRFENIDONE ADMINISTRATION (ROLLOVER STUDY)” eCRF form.

Pirfenidone will be taken orally in a daily dose of 2403 mg in divided doses three times per day with food. Study treatment should be titrated over 14 days, as tolerated, to the full dose of 9 capsules per day (three capsules TID), as follows:

- Days 1 to 7: one capsule TID (801 mg/day)
- Days 8 to 14: two capsules TID (1602 mg/day)
- Day 15 and continuing: three capsules TID (maximum of 9 capsules daily equal to 2403 mg/day).

Study treatment will continue until visit at Week 26 (\pm 1 week), unless terminated earlier for reasons described in Section 4.6.2 of the Protocol or patient is proceeding in the rollover study.

The total duration of exposure is defined as the time interval in weeks between the first dose and the last dose, inclusive, of study drug based on the patient study drug dosing information. Total duration (weeks) of exposure to study drug in the Treated set will be summarized by study period using descriptive statistics.

Exposure (duration of therapy during rollover study and overall up to 58 weeks) for patients in the rollover study will also be presented descriptively.

ML39355_STATISTICAL ANALYSIS PLAN_Final 2.0_17 June 2020

Descriptive statistics for Total number of capsules taken during the study period will also be presented.

All exposure data will be listed.

